1.1 Myopia is a major public health problem around the world

At present, myopia has become a major public health problem. World Health Organization (WHO) statistics show that there are about 75 million visual impairment patients in China, 2010, and uncorrected myopia is the first cause (42%). Over the past 50-60 years, the prevalence of myopia in East Asia such as China has risen rapidly, and the incidence of myopia shows a progressive trend after the onset of early age. In cities, the prevalence of myopia among middle school students is over 70%, and among high school graduates, 80-90% are myopia, of which 10-20% are high myopia. According to the degree of myopia, myopia above - 6D is defined as high myopia. The harm of high myopia mainly lies in its complications, some blinding eye diseases, such as macular degeneration and retinal detachment, are caused by corresponding changes of other tissues in the eye, and the quality of life of patients with high myopia is seriously affected. Morgan et al. pointed out in the comments of myopia experts published in Lancet in 2012 that the risk of complications such as posterior scleral staphyloma, choroidal neovascularization, retinal splitting and choroidal atrophy, which may cause blindness, has increased dramatically in a large number of new-onset high myopic people in Asia in the past 100 years. WHO has considered the prevention and treatment of myopia as part of the global blindness prevention plan, especially in East Asia. Recent epidemiological studies on ophthalmopathy show that with the improvement of the national ophthalmological service level, the rate of cataract surgery has increased rapidly, and the proportion of cataract-curable blindness in the population has continued to decline, while high myopia-Related retinopathy has gradually become the first irreversible blinding eye disease in China.

1.2 The overview of high myopia

From the occurrence of high myopia to pathological myopia and the final occurrence of blindness and visual impairment is a long-term process. First, myopia occurs in early childhood (the age of initial myopia is often before school age). The growth rate of myopia is significantly higher than that of most people. It often exceeds - 6D at the age of 15 (graduation from junior middle school). Secondly, unlike myopia in general children, myopia degree and axis length continue to progress in adulthood. With the extension of eye axis, posterior choroid and sclera continue to develop and become thinner. When pathological changes such as chorioretinal atrophy and choroidal neovascularization occur, they are generally over 50 years old. In order to avoid blindness and visual impairment caused by complications of high myopia, it is necessary to start myopia screening and intervention from childhood and adolescence.

1.3 Studies about atropine for controlling myopia progression

In order to reduce the incidence of high myopia, many myopia control interventions have been carried out in children and adolescents at home and abroad. Among them, atropine, an M-receptor antagonist, has been shown to be effective in myopia control in many experimental and clinical trials in recent years. In ATOM2 study in Singapore, a randomized controlled clinical trial was conducted. Two years after the use of 1% atropine eye drops, children's myopia decreased by 0.92D and eye axis increased by 0.4mm compared with the control group. After 2 years of treatment with 0.5%, 0.1% and 0.01% respectively, the myopia of children increased by 0.30D, 0.38D and 0.49D, respectively, which were

significantly lower than that of the control group (1.20D). Although 1% atropine eye drops had myopic rebound effect after discontinuation, the rebound effect disappeared when the concentration of atropine was reduced to 0.1% and 0.01%.

In the LAMP study in Hong Kong, after one year of treatment with 0.05%, 0.025% and 0.01% respectively, the myopia of children increased by 0.27D, 0.46D and 0.59D, which were significantly lower than that of the control group (0.81D), and the ocular axis increased by 0.20mm, 0.29mm and 0.36mm, respectively, which were lower than that of the control group (0.41mm). Similar studies at home and abroad have also confirmed that the use of low-concentration atropine has a good effect on myopia control. At present, in Taiwan, Hong Kong, Singapore and other Chinese areas, children with high myopia risk and rapid growth of myopia have been more commonly treated with low-concentration atropine eye drops for intervention.

The mechanism of atropine controlling myopia has not been fully elucidated. Early studies suggested that atropine could control myopia by regulating mechanism. However, McBrien found that atropine could still control the development of myopia after cutting off the regulating pathway through animal experiments. Therefore, the mainstream view is that atropine controls myopia by non-regulating mechanism. It may be through the antagonism of Mreceptor signaling pathway on the retina or scleral surface to slow down the development of myopia, but the specific mechanism has not yet been fully elucidated. Atropine eye drops belong to mydriasis and ciliary paralysis drugs. Long-term use of atropine eye drops can lead to symptoms such as dilatation of pupils, photophobia and blurring of close-range objects. These symptoms are closely related to drug concentration and frequency of use.

1.4 The objectives of our study

From previous studies, investigators can find that 1% atropine has good effect in early myopia control, but its side effects are great, long-term use compliance is poor, and there is a rebound effect; 0.01% atropine has poor effect in early myopia control, and the effect of follow-up for one year is not as good as 0.05%, but the effect of follow-up for two years is equal to 1%, that is, long-term use effect is good, and there are few side effects. Considering that only 1% or 0.01% atropine eyedrops (gels) are available in atropine eyedrops approved by the drug administration, investigators consider whether 1% atropine can be used for six months, and 0.01% atropine for one and a half years to achieve better early myopia control, late consolidation efficacy and side effects. In addition, the current clinical studies mainly focus on diopter and ocular axis. This project will explore the changes of lens and fundus after atropine treatment, whether there are indicators that reflect the effect of atropine control earlier and more accurately than diopter and ocular axis, and explore the target of atropine for myopia control.

2. Research Objectives

To explore a better way to control myopia progression and eliminate adverse effects at the same time;

To provide reliably evidence for clinical guideline of atropine use in children;

To investigate the mechanism of atropine on eyes.

3.Trail Design

a randomized controlled, prospective cohort study, no mask.

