3.2 Groups and Sample size

Myopic children aged from 7-12 years old are randomly allocated into two groups: combined use of atropine sulfate 1% ophthalmic ointment and atropine sulfate 0.01% eye drop (experimental group) and atropine sulfate 0.01% eye drop (control group). Each group includes 111 participants.

3.3 Medications and usage:

3.3.1 control group: atropine sulfate 0.01% eye drop, once a day, once a drop, for two years;

3.3.2 Combined application group: atropine sulfate 1% ophthalmic ointment, once a day for the first week, once a drop for both eyes; and then once a week, once a drop for both eyes for half a year. Half a year later, atropine sulfate 0.01% eye drop is used once a day, one drop each time, with both eyes for one and a half years. Usage: Drop it into conjunctival sac, about the size of a rice grain, press the nasal root with thumb and index finger for 2 minutes after dripping, and use it before going to bed. Patients once a week are advised to use it before going to bed on Friday night.

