3.4.2.12 Wide angle OCT/OCTA (Zeiss-9000) Wide-angle OCT/OCTA examinations were performed after cycloplegia. OCT/OCTA location: macular + optic disc area. Shooting mode: 12*12mm, 15*9mm angio mode; 16mm loop sweep mode (horizontal and vertical directions) a total of 8 scans. Shooting requirements: communicate more with the subject; the forehead and chin must be close to the instrument. If the image quality is affected by blinking or eye movement during shooting, participants need to re-shoot. This item is optional for children under 6 years old.

3.4.3 Questionnaire: The questionnaire is about the time children spend on outdoor activities and near work.

4. Follow up

4.1 Frequency: Combined use of 1% atropine and 0.01% atropine group is followed up after first week, then every three months. 0.01% atropine group is followed up every three months.

4.2 Examinations:

4.2.1 First week follow up for combined use group: accommodation, near vision acuity > mesopic pupil size > Autorefraction and subjective refraction > IOL-Master, Pentacam, Swept-source optical coherence tomography (SS-OCT, Topcon), wide-angle optical coherence tomography angiography(OCTA,Zeiss-9000)

4.2.2 Every three months: accommodation, near vision acuity > mesopic pupil size > slit lamp anterior segment examination > cycloplegia > Autorefraction and subjective refraction > IOL-Master, Pentacam, Swept-source optical coherence tomography (SS-OCT, Topcon), wide-angle optical coherence tomography angiography(OCTA,Zeiss-9000)

5. Statistical Analysis

5.1 Descriptive statistics A. Continuity variables: sample size, mean, standard deviation, minimum, maximum, quartile B. Classification variable or grade variable: frequency distribution

5.2 statistical methods A. Continuous variables: The normality test uses the Kolmogorov-Smirnov test. If the normal distribution is satisfied, the t test or one-way ANOVA is used; if the normal distribution is not satisfied, the Mann-Whitney U test or the Kruskal Wallis test is used. The two-two comparison between groups was performed using the Bonferroni method. B. Categorical variable: chi-square test. C. Correlation analysis:

simple linear regression and stepwise multiple linear regression, using nonlinear regression if necessary.

5.3 Statistical significance All differences were statistically defined as $P < 0.05$ (bilateral)

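### The marker question in section 1.4 is comparative, but section 5.2C specifies no comparison of a lens or fundus marker with same-visit refraction and axial-length change

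*Combined protocol and SAP*

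**What the plan says.** Section 1.4 states, as an exploratory aim, "This project will explore the changes of lens and fundus after atropine treatment", and then asks "whether there are indicators that reflect the effect of atropine control earlier and more accurately than diopter and ocular axis". Section 2 does not list this question; its nearest objective concerns the mechanism of atropine.

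For relationships between variables, section 5.2C gives one line under correlation analysis: "simple linear regression and stepwise multiple linear regression, using nonlinear regression if necessary". Section 5.3 sets a two-sided 5% level. Section 5.4 uses diopter, axial length and fundus structure to form subgroups, not as competing predictors.

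On numbers, section 3.2 says "Each group includes 111 participants", in two groups. On timing, section 4.1 says "Combined use of 1% atropine and 0.01% atropine group is followed up after first week, then every three months"; the control group has three-monthly visits only. Section 4.2.2 schedules refraction, IOL-Master, Pentacam, SS-OCT and OCTA together at each three-monthly visit.

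**The concern.** The question asks whether something is better than a named standard, so it needs an analysis in which marker and standard face each other. Section 5 specifies none. It also gives no target against which accuracy is judged. Myopia control is itself measured by refraction and axial length, so being more accurate than those measures has meaning only against a later outcome, such as subsequent progression.

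Without a stated comparison, the analyst is left with slopes tested against zero or with whatever a stepwise procedure keeps. A marker could be significant on either count and still predict progression less well than axial-length change measured on the same day. At stake is the marker conclusion: the trial could report associations and have nothing that answers the question it posed.

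**Working it through.** **Inputs.** From the documents: 111 per group, 222 in total (3.2); two-sided 0.05 (5.3); month 3 as the first visit common to both arms (4.1). Assumed, because the documents give none: all correlations, 20% loss (222 × 0.8 ≈ 178 children), and the axial growth and error SDs in step 5. The plan's 111 cannot be reproduced, since no effect size, SD, power or dropout is stated; the steps below do not need it.

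**1. Smallest significant correlation.** |r| = t/√(n − 2 + t²), with t the 0.975 quantile on n − 2 degrees of freedom.
- n = 222: 1.971/√(220 + 3.884) = 0.132, R² = 1.7%.
- n = 178: 0.147, R² = 2.2%.
- One arm, n = 111: 0.187, R² = 3.5%.

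These depend only on n and alpha.

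**2. A weak marker that adds nothing to the benchmark.** Let the marker correlate r = 0.2 with later progression and early axial-length change correlate 0.5, 0.6 or 0.7. The marker adds nothing when its correlation with the benchmark is 0.2/0.5 = 0.40, 0.2/0.6 = 0.33 or 0.2/0.7 = 0.286. In 10,000 simulated data sets per scenario at n = 222:
- significant alone: about 85% (Fisher-z power for r = 0.2 is also 85%);
- significant with the benchmark in the model: about 5%;
- better than the benchmark by Williams' test of dependent correlations: 0%;
- significantly worse: 99.5% to 100%.

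At n = 178 the figures are about 77%, 5%, 0% and 98% to 100%.

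**3. Retention is not superiority.** Marker r = 0.5, benchmark r = 0.7, mutual r = 0.5, n = 222: the marker is significant beside the benchmark in 95.5% of data sets and significantly worse than it in 98.4%. Alone it explains 25% of variance against 49%.

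**4. Can a head-to-head test succeed?** With marker 0.7 against benchmark 0.5 (mutual r = 0.4), superiority is shown in 96.8% at n = 222 and 92.5% at n = 178. With 0.7 against 0.6 it is shown in 53.8% and 44.6%. Clear superiority is detectable; a small advantage often is not.

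**5. Choice of outcome window.** Assume early (0–3 month) growth SD 0.02 mm, late growth SD 0.14 mm independent of it, and error SD s at each visit. Month-3 change has variance 0.0004 + 2s².
- Against 0–24 month change: r = (0.0004 + s²)/√[(0.0004 + 2s²)(0.0200 + 2s²)].
- Against month 3–24 change: r = −s²/√[(0.0004 + 2s²)(0.0196 + 2s²)].

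If instead true early and late growth correlate 0.6, their covariance is 0.6 × 0.02 × 0.14 = 0.00168. The month 3–24 numerator becomes 0.00168 − s², or 0.00168 if the errors are not shared.

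| s (mm) | No tracking, 0–24 | No tracking, 3–24 | Tracking 0.6, 3–24 | Tracking 0.6, errors not shared |
|---|---|---|---|---|
| 0.01 | 0.14 | −0.03 | 0.46 | 0.49 |
| 0.02 | 0.16 | −0.08 | 0.26 | 0.34 |
| 0.03 | 0.19 | −0.13 | 0.11 | 0.24 |

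The 0–24 window flatters early axial-length change, because the early interval and the baseline error are part of the outcome. The 3–24 window handicaps it, because the month-3 error enters both terms with opposite signs. With no tracking, the negative correlations would be falsely significant at n = 222 in about 7%, 22% and 50% of trials.

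**6. Several markers.** Ten independent null markers at 0.05 give 1 − 0.95¹⁰ = 40% chance of at least one false positive. The Bonferroni step in 5.2A covers pairwise group comparisons, not a list of markers.

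**The case against.** The strongest defence is that the plan is silent, not wrong. Stepwise multiple regression can hold early refraction and axial length beside a marker. The between-group tests in 5.2A, applied visit by visit, would show descriptively when the arms separate on each measure, which bears on the word earlier. The aim is exploratory and outside the formal objectives in section 2.

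Much of this stands. A reader might infer that the plan excludes a comparison, or that it will call any marker with a significant slope useful. The documents support neither: 5.2C names no marker, outcome or decision rule, and 5.3 only fixes a significance level.

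The gap remains all the same. The plan does not say that the benchmark will enter the stepwise model, and step 3 shows that retention would not establish greater accuracy. Separation of the arms on one measure and not another at a given visit is not a test between the measures. Before month 3 there are no control-group data to compare.

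A further fair objection concerns the remedy. The question is about reflecting the effect of atropine, and a model with arm in it removes the between-arm part of that effect. A marker that captured the effect fully could then appear to add nothing. This stands, and the fix allows for it.

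**Conclusion.** The point holds as a gap in the analysis plan for an exploratory aim: the question is comparative and no comparison is specified. The firm figure is the threshold: |r| of 0.132 (1.7% of variance) is significant with 222 children, and 0.147 with an assumed 178. The percentages in steps 2 to 4 and the window effects in step 5 rest on assumed correlations and SDs and are illustrations.

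Two stronger readings are tempting. One is that a far poorer marker would pass; how much poorer depends wholly on the assumed strength of early axial-length change, for which the documents give no figure. The other is that moving the outcome to month 3–24 removes the overlap problem; step 5 shows that the bias changes sign instead. Nothing here touches the randomised treatment comparison. The change is worth making because the data for it will exist in both arms.

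**What to change.** Add to 5.2C:

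1. A short list of lens and fundus markers fixed before analysis, taken at month 3 (the first visit common to both arms) and repeated at month 6.
2. A head-to-head comparison of each marker with same-visit change in axial length and in refraction, for predicting later axial-length and refraction progression. Use the difference in cross-validated R², or a test of dependent correlations, with a confidence interval and multiplicity control across markers.
3. Results with and without arm in the model, because the aim concerns the treatment effect.
4. Both outcome windows (from baseline and from the predictor visit), or an outcome that starts at a visit after the one supplying the predictor, so that no measurement error is shared. A later start leaves out part or all of the half-year 1% phase in section 3.3.2, and the report should say so.
5. Wording rules: reserve more accurate for a marker that beats the benchmark, and call one that only adds to it complementary.

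If this is not wanted, restate the aim in 1.4 as exploratory association.

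The cost is SAP text and some analysis time; no new data are needed. Fewer markers will qualify, and a marker with only a small true advantage may not be shown to have one (step 4).

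### Eliminating adverse effects is part of the first objective, but photophobia, other symptoms, systemic events and stopping for side effects are not recorded, so it can be answered only in part

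*Combined protocol and SAP*

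**What the plan says.** The first of three objectives in section 2 joins efficacy and harm: "To explore a better way to control myopia progression and eliminate adverse effects at the same time". Section 1.4 gives the reason for the sequential regimen. It says of 1% atropine that "its side effects are great, long-term use compliance is poor", and it asks whether six months of 1% followed by eighteen months of 0.01% can be used "to achieve better early myopia control, late consolidation efficacy and side effects". Section 1.3 lists what to expect from long-term use, "symptoms such as dilatation of pupils, photophobia and blurring of close-range objects", and ties these effects to concentration and frequency of dosing.

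The follow-up visits are itemised. Section 4.2.1 begins "First week follow up for combined use group: accommodation, near vision acuity > mesopic pupil size > Autorefraction and subjective refraction" and then goes on to biometry and imaging. Section 4.2.2 begins "Every three months: accommodation, near vision acuity > mesopic pupil size > slit lamp anterior segment examination > cycloplegia" and continues in the same way. The methods for accommodation, near acuity and pupil size are in 3.4.2.3 and 3.4.2.4. The only questionnaire (3.4.3) covers outdoor time and near work; it is a step in the examination process of 3.4.1 and appears in neither follow-up list. The only instruction about symptoms (3.4.2.6) concerns discomfort during cycloplegia, which is to be examined and treated. Section 5 gives general methods for continuous and categorical variables and names no safety outcome.

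**The concern.** The argument for the combined regimen is better control at a tolerable cost in side effects. Tolerability has two sides: what the eye does, which instruments can read, and what the child experiences and whether the child keeps using the treatment, which has to be asked. The visit lists cover the first side only. A larger pupil does not show whether a child had photophobia, or stopped treatment because of it.

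The readings are also snapshots. After the first week the combined arm uses 1% weekly (3.3.2), and nothing fixes the visit day relative to the last dose, so effects between visits are missed unless someone asks. Symptoms and reasons for stopping that are not recorded at the time cannot be reliably recovered at analysis. A conclusion that the regimen is well tolerated, offered as evidence for a guideline in children (the second objective), would lack part of its basis.

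**Working it through.** **Step 1: set the effects of interest against the visit lists.** The first three rows are the effects named in 1.3. The others are general tolerability items implied by the objective.

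| Effect | Week 1 (4.2.1, combined arm only) | Three-monthly (4.2.2, both arms) |
|---|---|---|
| Pupil dilatation | Mesopic pupil size | Mesopic pupil size |
| Near blur | Accommodation, near acuity | Accommodation, near acuity |
| Photophobia | None | None |
| Local or allergic reaction | None | Slit lamp only, for visible anterior-segment signs |
| Systemic events, other symptoms | None | None |
| Stopping because of side effects | None | None |

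Of the three named effects, two have an objective measure at every follow-up visit and one, photophobia, has none.

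**Step 2: what the scheduled measurements can show.** The input is 111 per arm (3.2), two-sided alpha 0.05 (5.3), and no dropout (assumed). The detectable standardised difference is d = √(2/111) × (z for alpha + z for power).

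- 80% power: 0.1342 × (1.960 + 0.842) = 0.376 SD
- 90% power: 0.1342 × (1.960 + 1.282) = 0.435 SD

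Pupil size, accommodation and near acuity can therefore be compared between arms with reasonable precision. The documents give no basis for the 111 (no effect size, SD, power or dropout), so that figure cannot be reproduced and is taken as given.

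**Step 3: what a symptom and adverse-event form could show.** All event rates here are assumptions, because the documents give none.

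- Probability of at least one case in an arm, 1 − (1 − p)^111:
  - p = 1%: 1 − 0.99^111 = 67%
  - p = 2%: 1 − 0.98^111 = 89%
  - p = 5%: 1 − 0.95^111 = 99.7%
- No cases in 111, one-sided 95% upper limit: 1 − 0.05^(1/111) = 2.7%
- Half-width of the 95% CI for 20% versus 5%: 1.96 × √(0.20 × 0.80/111 + 0.05 × 0.95/111) = 0.085, or 8.5 percentage points
- Power of a two-sided comparison of proportions (normal approximation): 93% for 5% versus 20%, 84% for 10% versus 25%, 55% for 10% versus 20%

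The trial is large enough to describe common side effects and to detect large differences between arms, but not modest ones. For the unmeasured effects, what is missing is the record.

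**The case against.** The strongest reply is that the plan does measure side effects. Pupil dilatation is read directly and near blur through accommodation and near acuity, every three months in both arms and also at week 1 in the combined arm. Slit lamp examination every three months can pick up visible anterior-segment reactions. The general methods in 5.2 are enough to compare these readings by arm. All of that stands.

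It rules out some stronger readings. A reader might infer that the trial cannot address adverse effects at all, or that half of its main question is lost. The documents do not support this: two of the three named effects are scheduled at every follow-up visit, and section 2 lists three objectives without ranking one as main. Nor would all harms on 1% atropine go unrecorded, and it is too absolute to say that no allergic reaction could be noticed.

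The reply does not fill the remaining gap. Photophobia, systemic events, other symptoms and reasons for stopping have no planned record. Slit lamp is absent from the week-1 list, and no rule says how its findings are to be recorded.

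A second objection is that self-reported symptoms in an unmasked trial are open to bias, and that the combined arm's extra week-1 visit gives it one more occasion to report. Both points are fair. They bear on how the form is used and analysed, not on whether to have one.

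**Conclusion.** The concern holds in limited form. The adverse-effect part of the first objective can be answered for pupil size, accommodation, near acuity and visible anterior-segment findings. It cannot be answered for photophobia, other symptoms, systemic events or stopping because of side effects, and no safety outcome is defined. The efficacy comparison is unaffected.

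The omission is in the plan itself: the visit lists, the questionnaire description and section 5 are all present and itemised. The 99.7%, 89%, 2.7% and ±8.5-point figures are illustrations that rest on assumed rates and on 111 evaluable children per arm; any dropout would weaken them. They apply only to the effects with no planned measure. The change should be made, because it is cheap and missing symptom data cannot be restored later.

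**What to change.** - **4.2.2:** add a one-page symptom and adverse-event form, worded identically and asked at the same three-monthly visits in both arms, with the same recall period. Items: photophobia, near blur, local or allergic reaction, systemic symptoms, and whether treatment was stopped and why.
- **4.2.1:** use the same form at week 1, but report it descriptively for the combined arm only and leave it out of the between-arm comparison. The control arm has no week-1 visit, so including those answers would give the arms unequal chances to report.
- **Section 5:** name the safety outcomes. Compare the arms by period, months 0–6 and months 6–24, on the proportion with each symptom and the proportion stopping because of side effects, alongside pupil size, accommodation and near acuity. A single ever-affected proportion over two years would merge the 1% and 0.01% phases and could not show whether effects resolve after the switch. Give differences with 95% CIs, so that absence of harm is not inferred from P > 0.05.

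The cost is one or two minutes per visit at visits already planned, plus one table. Self-report in an unmasked trial should be stated as a limitation. No dose or treatment rule changes.

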3.4 Examination

3.4.1. Examination process: The brief process is as follows: Identity information registration > height, weight > naked eye vision & wearing vision > intraocular pressure > accommodation, near vision acuity > mesopic pupil size > slit lamp anterior segment

examination > cycloplegia > Autorefractometry and subjective refraction > IOL-Master, Pentacam, Swept-source optical coherence tomography (SS-OCT, Topcon), wide-angle optical coherence tomography angiography(OCTA, Zeiss-9000)> fill out the questionnaire.

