3.4.2.6 Cycloplegia The cycloplegia procedure is as follows: 1 drop of 0.5% proparacaine (Alcaine, Alcon) is added to the conjunctival sac of each eye, and 1 drop of 1% cyclopentolate is added to each eye after 15 seconds. (Cyclogyl, Alcon), 5 minutes apart. After each drip, ask the participant to press the inner canthus for a few seconds gently and try to take the head back posture. The last drop of cyclopentolate was instilled into the conjunctival sac for 30 minutes to check for light reflection. If the light reflection disappeared and the pupil diameter was greater than 6 mm, cycloplegia was considered complete. If the light reflection still exists, add a third drop of cyclopentolate, and re-

examine the light reflection and pupil diameter after 20 minutes. If there was still light reflection, the inspector needs to record this. During cycloplegia, if the participant has symptoms of ocular discomfort, the ophthalmologist should carefully examine it and give an appropriate treatment.

3.4.2.7 Axis measurement: The axial measurement was performed using an IOL Master (version 5.02, Carl Zeiss Meditec, Germany). Simulated eye calibration was needed before measurement. Each eye was measured repeatedly for 3 times, and the difference was less than 0.02 mm each time. For those who still have large fluctuations in multiple measurements, the examiner needs to record it.

3.4.2.8 Measurement of refractive state and corneal radius of curvature (CR) The refractive status and CR measurements were performed using an automated computer refractometer (KR-8900, Topcon, Japan), which was performed after ciliary muscle paralysis. Simulated eye calibration needed before measurement. Each eye was repeatedly measured three times to average, and if any two results differ by more than 0.5 D, the measurement needed to be repeated. If there were still significant differences in the results of multiple measurements, the examiner needed to record it.

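### The plan masks no one, not even outcome assessors or image readers, although at baseline and the three-monthly visits the main eye measurements follow cycloplegia in both arms

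*Combined protocol and SAP*

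**What the plan says.** Section 3 gives the design in one line: "a randomized controlled, prospective cohort study, no mask". No other section masks examiners, image readers or analysts, or says why masking them was not possible.

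The order of tests is set out in three places:

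- **Baseline (3.4.1):** "cycloplegia > Autorefractometry and subjective refraction > IOL-Master, Pentacam, Swept-source optical coherence tomography (SS-OCT, Topcon", followed by wide-angle OCTA.
- **Three-monthly visits (4.2.2):** "slit lamp anterior segment examination > cycloplegia > Autorefraction and subjective refraction > IOL-Master, Pentacam, Swept-source optical coherence tomography", again followed by OCTA. Accommodation, near acuity and mesopic pupil size come before this sequence.
- **Week 1 (4.2.1):** "4.2.1 First week follow up for combined use group: accommodation, near vision acuity > mesopic pupil size > Autorefraction and subjective refraction > IOL-Master", then Pentacam and OCT/OCTA. No cycloplegia step is listed. Only the combined arm attends; for the other arm, Section 4.1 says "0.01% atropine group is followed up every three months".

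Section 3.4.2.6 defines the target state: "If the light reflection disappeared and the pupil diameter was greater than 6 mm, cycloplegia was considered complete". If the reflex persists after an extra drop, the instruction is only to note it: "If there was still light reflection, the inspector needs to record this".

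**The concern.** Families cannot easily be masked when one arm starts on an ointment and the other on a drop, with different frequencies (Section 3.3). That explains open treatment. It does not explain leaving the people who take and read the measurements unmasked.

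Section 1.3 says that pupil dilation and near blur depend on concentration and frequency of use. Staff at the accommodation, near-acuity and pupil steps may therefore infer the arm. After cycloplegia that cue should largely be gone, and this is where refraction, axial length and the imaging measures are taken.

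An operator or reader who knows the arm can influence when a reading is repeated, which scan is accepted, or how an image is measured. A shift that arises in this way is not removed by randomisation and does not shrink with more children. Section 2 says that the trial is meant to supply reliable evidence for clinical guidance, so protection that costs little is worth having.

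**Working it through.** **1. Where masking is plausible.** Setting the visit sequences side by side:

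| Visit | Arms attending | Cycloplegia listed before refraction, IOL-Master, Pentacam, OCT/OCTA |
|---|---|---|
| Baseline (3.4.1) | both | yes |
| Week 1 (4.2.1) | combined only | no |
| Every three months (4.2.2) | both | yes |

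The visits at which the arms can be compared are the first and third rows, and both have cycloplegia first. Week 1 has no comparator. From half a year onward both arms use the 0.01% drop once a day (Section 3.3), so any visible drug difference should fade further over the last year and a half.

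**2. How much discretion the operators have.**

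- *Refraction (3.4.2.8):* automated, three readings averaged, repeated if any two differ by more than 0.5 D. Persistent differences are recorded.
- *Axial length (3.4.2.7):* three readings with a 0.02 mm tolerance. Persistent fluctuation is recorded.
- *Subjective refraction (3.4.2.9):* required when acuity is below 0.8 (0.63 at age 6 and under), to obtain best-corrected acuity. The visit sequences list it without that condition.
- *SS-OCT (3.4.2.11):* signal floors of 50 (3D) and 60 (radial), and a quality floor of 90 for the colour photograph, with retakes.
- *Wide-angle OCT/OCTA (3.4.2.12):* retakes for blinking or eye movement, with no numeric floor.

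No section limits the number of repeats or says which set of readings is kept. No section describes how the images are measured, or by whom. Discretion is therefore narrow for refraction and axial length and wider for the images.

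**3. Illustration of size.** The only design figure in the plan is 111 per group (Section 3.2). It cannot be reproduced, because no effect size, SD, power or dropout is given; the point does not rest on it. With no SD available, the work is in SD units.

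- Inputs: n = 111 per arm (3.2); two-sided 5% level (5.3). The shift b is **assumed**.
- Standard error of the arm difference: √(2/111) = 0.134 SD.
- False-positive rate with no true effect and a systematic shift b: Φ(b/0.134 − 1.96) + Φ(−b/0.134 − 1.96).
- For b = 0.1: b/SE = 0.745, so Φ(−1.215) + Φ(−2.705) = 0.112 + 0.003 ≈ 0.116.

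| Assumed shift b (SD) | False-positive rate |
|---|---|
| 0 | 5.0% |
| 0.05 | 6.6% |
| 0.1 | 11.6% |
| 0.2 | 31.9% |

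For scale, 111 per arm gives 80% power for (1.96 + 0.84) × 0.134 ≈ 0.376 SD, so a shift of 0.1 SD is about 27% of that difference (0.1/0.376).

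**The case against.** The design is openly declared as unmasked, and nothing in it is internally wrong on this point. Refraction and axial length come from automated instruments with numeric repeat rules and simulated-eye calibration. Those rules restrict judgement, and the axial tolerance leaves little room to choose between readings. Nothing in the documents supports a shift of any particular size. All of this stands, and it limits the point to an improvement.

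Three stronger readings are tempting, and the documents do not support them:

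- *That all of these measures follow cycloplegia.* The week-1 sequence lists them without it, in one arm only. Equal dilation elsewhere is expected but not assured, since a persisting reflex is only recorded.
- *That operators could be masked without extra staff.* Staffing is not described. The same refractometer model, KR-8900, is named for pupil size before cycloplegia (3.4.2.4) and for refraction after it (3.4.2.8). If one operator does both, that person sees the undilated pupil. Coded image measurement by the same readers does not depend on this.
- *That the shift can be judged against a 0.21 D gap taken from Section 1.3*, that is 0.49 − (1.20 − 0.92). Those figures compare two years of 1% with two years of 0.01%, not half a year of 1% followed by 0.01%. Section 1.4 itself treats the two-year effects as equal.

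What survives the objection is that repeats, retakes, unresolved variation, subjective refraction and image measurement still leave room for knowledge of the arm to act.

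**Conclusion.** The point holds as a modest, inexpensive improvement. The plan has no masking of any role. At baseline and at the three-monthly visits the main measurements follow cycloplegia in both arms, so pupil size should largely not give the arm away there. Week 1 is the exception. The false-positive figures, such as 11.6% at 0.1 SD, are arithmetic on assumed shifts. They show what a small systematic difference would do at this sample size, not that one will occur. The case is strongest for image measurement, where the plan gives no reading rules, and weakest for axial length. A reader should not infer that the trial's results would be invalid without the change.

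**What to change.** In Section 3, replace the statement of no masking with: participants and treating staff unmasked; image readers and, where tasks can be separated among existing staff, post-cycloplegia examiners masked to arm. To support this:

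- keep the arm off examination forms and device IDs, using the study code only;
- measure OCT/OCTA and Pentacam images under code, without arm labels;
- where possible, have a different existing operator do the pupil and accommodation tests before cycloplegia;
- ask families not to mention treatment during examinations.

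The cost is protocol wording, coding of forms and images, and some allocation of tasks. No treatment, visit or test changes. The downside is that masking will be imperfect: children may disclose treatment, incomplete cycloplegia is only recorded, and the week-1 visit exists in one arm only. If staff cannot be separated on site, masking is limited to coded image reading, and the protocol should state that limit.
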